#### 6.3.2. Exclusion criteria

- Age < 18 years
- Obvious pregnancy
- Known preexisting Do Not Attempt Resuscitation order

## 6.3.3. Investigation population

The goal is to include 40 patients (30 randomized to DSD and 10 to standard treatment). The 3:1 ratio was chosen since our main focus in this pilot study is the interventional treatment but also to evaluate the randomization process and adherence to protocol.

# 6.3.4. Criteria and procedures for subject withdrawal or discontinuation.

If DSD by any reasons cannot be performed due to any expected/unexpected circumstances at the scene EMS shall at once proceed with standard defibrillation according to routine practice. All randomized patients will be included in the ITT analysis.

#### 6.4. Methods to minimize bias

Study participants will be randomized at the individual patient level, therefore minimizing confounding and allocation bias.

Due to the nature of the intervention, blinding is not possible for providers, therefore there is a theoretical risk for performance bias (duration of CPR). All clinical endpoints and follow-up will be collected by a research staff in a blinded way.

Version No: 1.1

Date: 2024-10-27 27 (48)

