## 6.5. Unblinding

This is an open label pilot trial. The neurological follow-up will be performed in a blinded way. That is the persons collecting the follow-up data at 30, 90 and 180 days will not be aware of the randomized allocation.

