# 6.6. Description of the clinical procedures and diagnostic methods relating to the clinical investigation

[figure not shown]
The study is conducted in the prehospital emergency medical services, i.e. ambulance organizations. The trial will be conducted by participating ambulance units attending OHCA's. These units will perform screening for inclusion, randomization, intervention or control treatment and initial follow-up. All ambulance units in Sweden follow European resuscitation council (ERC) guidelines published in 2021 [4] and perform team training on an annual basis for high quality provision of ACLS care in OHCA.

In clinical practice a cardiac arrest is confirmed by the absence of consciousness and absence of normal or no breathing. In this clinical situation cardiac arrest shall be suspected and CPR initiated. In all cases of OHCA a defibrillator should always be attached with the standard pad placement first (A-L position) in accordance with standard of care and ERC guidelines. If there is VT/VF or an AED suggests defibrillation, defibrillation should be performed, and immediate chest compressions resumed.

Thereafter, the patient can be screened for inclusion. If two defibrillators study specific defibrillators on site, and no exclusion criteria the patient can be included and randomized. Randomization will be performed by drawing a scratch-card with concealed allocation that will be stored with the EMS defibrillators. All scratch-cards will be pre-randomized in a 3:1 ratio in blocks consisting of 4-8-12 and stratified by region and ambulance provider.

Version No: 1.1

Date: 2024-10-27 28 (48)

OHCA = Out of Hospital Cardiac Arrest, VT/VF = pulseless Ventricular Tachycardia / Ventricular Fibrillation, CPR = Cardiopulmonary Resuscitation, DSD = Double Sequence Defibrillation, CRF = Clinical Report Form

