#### 8.1 Prehospital CRF1, Characteristics during the resuscitation phase

After completing the care of the patient, the study responsible EMS-unit will report a digital prehospital CRF. This is practically done by using and reading a study specific QR-code located on the back of the specific randomization envelope / sheet using a smart-phone. This will open a webpage automatic registration of time of registration and information to be filled in when opened.

Version No: 1.1

Date: 2024-10-27 33 (48)

The prehospital CRF will contain basic on-site information such as which ambulance that performed randomization, randomization study number, time and date of cardiac arrest, number of shocks prior to EMS arrival and number of shocks prior to randomization, treatment allocation, electrode placement for each defibrillation, number of defibrillations before DSD, ROSC and if the patients survived the event. Furthermore, if the patient has a known identity, personal id-number will be included to enable follow up. If the patients do not have a known identity a temporary identification number will be used.

The prehospital CRF allows for real-time monitoring of randomization and allows for early start of follow-up.

Other core resuscitation characteristics will later be reported and collected from the SRCR part 1 and ambulance charts. This registry data is standard and mandatory for all EMS personal to report and contains resuscitation and patient characteristics and reporting to the register is part of routine documentation.

ECG files from defibrillators. All data stored in the defibrillators after each use in the trial will be exported to a secure server and analyzed for defibrillation safety and CPR quality.

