#### 8.3 Neurological and patient reported Follow up CRF, 30, 90 and 180 days

For patients who survive to hospital discharge and have signed an informed consent to further participation in the trial a specific follow-up team separated and blinded from the care and randomized allocation (intervention or control) will be responsible for neurological follow-up. Neurological function will be assessed according to the modified Ranking Scale (mRS) and the Cerebral Performance Category (CPC) scale at 30, 90 and 180 days. The mRS scale includes categories 1-6, where higher numbers indicate more severe

0 = no symptoms,

disability.

- 1 = no significant disability—able to carry out all usual activities, despite some symptoms,
- 2 = slight disability—able to look after own affairs without assistance but unable to carry out all previous activities,
- 3 = moderate disability—requires some help but able to walk unassisted,
- 4 = moderately severe disability—unable to attend to own bodily needs without assistance and/or unable to walk unassisted,
- 5 = severe disability—requires constant nursing care and attention, bedridden, incontinent,

Version No: 1.1

Date: 2024-10-27 34 (48)

and 6 = dead.

The CPC scale includes categories 1-5, where higher numbers indicate more severe neurological impairment;

- 1 = Conscious, alert, able to work and lead a normal life. May have minor psychologic or neurologic deficits (mild dysphasia, non-incapacitating hemiparesis, or minor cranial nerve abnormalities),
- 2 = Conscious. Sufficient cerebral function for part-time work in sheltered environment or independent activities of daily life (dress, travel by public transportation, food preparation). May have hemiplegia, seizures, ataxia, dysarthria, or permanent memory or mental changes, 3 = Conscious. Dependent on others for daily support (in an institution or at home with exceptional family effort). Has at least limited cognition. This category includes a wide range of cerebral abnormalities, from patients who are ambulatory but have severe memory disturbances or dementia precluding independent existence, to those who are paralyzed and
- 4 = Unconscious. Unaware of surroundings, no cognition. No verbal and/or psychologic interaction with environment, and
- 5 = Brain dead, circulation preserved. Death at discharge.

can communicate only with their eyes, as in the "locked in" syndrome,

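### Section 6.4 says all clinical endpoints are collected blinded, but ROSC is recorded by the unblinded crew that gave the treatment

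*Protocol*

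**What the plan says.** Section 6.4 (Methods to minimize bias) first concedes that "Due to the nature of the intervention, blinding is not possible for providers" and names performance bias as the resulting risk. It then states without qualification that "All clinical endpoints and follow-up will be collected by a research staff in a blinded way".

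The next section, 6.5, is narrower: "This is an open label pilot trial. The neurological follow-up will be performed in a blinded way". It explains this as meaning that "the persons collecting the follow-up data at 30, 90 and 180 days will not be aware of the randomized allocation". The section on neurological and patient-reported follow-up agrees: for consenting patients who survive to discharge, "a specific follow-up team separated and blinded from the care and randomized allocation (intervention or control) will be responsible for neurological follow-up".

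On prehospital data, section 6.6 says of the ambulance units: "These units will perform screening for inclusion, randomization, intervention or control treatment and initial follow-up". The section on the prehospital CRF1 adds: "After completing the care of the patient, the study responsible EMS-unit will report a digital prehospital CRF". That form includes "number of shocks prior to EMS arrival and number of shocks prior to randomization, treatment allocation, electrode placement for each defibrillation", and also ROSC. The same section says that EMS personnel report the resuscitation registry data (SRCR part 1).

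The secondary endpoints in the synopsis and section 6.2.2 are the proportion with sustained ROSC and the number of defibrillations to sustained ROSC.

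**The concern.** A blinding statement tells the reader which outcomes are protected from detection bias. Section 6.4 extends that protection to every clinical endpoint, while the data-collection sections give the earliest clinical outcome to people who know the arm because they delivered it.

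Sustained ROSC leaves some room for judgement. The synopsis places it at hospital arrival, section 6.2.2 gives no time point, and neither says how long circulation must hold to count as sustained. A crew that has just delivered a novel double-shock strategy may make that call differently from one that has not, even in good faith.

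At stake is what the pilot report can say about its ROSC comparison. Section 7.3 plans between-arm differences in proportions with 95% confidence intervals, and section 7.4 says the results will inform the main study's sample size. If the sentence stands, the report and the main protocol may both describe ROSC as blinded when it was not.

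**Working it through.** No formula applies. The protocol gives no figure on this point, so the check sets the blinding statements against the data flow for each clinical endpoint.

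**Step 1: who is blinded.** Section 6.4 says research staff, for all clinical endpoints. Section 6.5 and the neurological follow-up section say the team working at 30, 90 and 180 days. No section describes a blinded collector of prehospital outcomes.

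**Step 2: who collects the prehospital outcomes.** Section 6.6 gives randomization, treatment and initial follow-up to the same ambulance units, and lists CRF1 and SRCR part 1 as the follow-up done straight after resuscitation. The CRF1 section names the EMS unit as the reporter. Section 6.4 itself says these providers cannot be blinded.

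**Step 3: what they record, endpoint by endpoint.**

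| Clinical endpoint | Source described | Blinded as described? |
|---|---|---|
| Sustained ROSC (secondary) | ROSC is a CRF1 item beside the allocation; SRCR part 1 is also crew-reported | No |
| Defibrillations to sustained ROSC (secondary) | The total is not a named CRF1 field; CRF1 has ROSC and electrode placement per shock; device files are exported | The endpoint depends on the ROSC call, which is not blinded |
| mRS, CPC and quality of life at 30, 90 or 180 days (tertiary) | Separate follow-up team | Yes |

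Survival to admission, discharge and 30 days is left aside: it is hard to misclassify and is not part of this point.

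**Step 4: is there another source that restores blinding?** Section 8.1 (Data collection) also lists ECG files and ambulance charts. The CRF1 section says stored defibrillator data are exported and analyzed for defibrillation safety and CPR quality, and section 14.3 adds that energy delivery is checked at each defibrillation. This is an objective record of shocks, but it is not named as the source for ROSC or for the shock endpoint, nor said to be read blind. A DSD trace can also reveal the arm.

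**Step 5: scale.** With the planned 30 and 10 patients (section 6.3.3), one changed ROSC classification moves the DSD proportion by 1/30 = 3.3 points and the control proportion by 1/10 = 10 points. These are the step sizes of any binary outcome in arms of this size. They say nothing about how often misclassification would occur.

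**The case against.** The case for leaving the text alone has several parts.

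- **The trial is openly open-label.** Section 6.4 says providers cannot be blinded immediately before the disputed sentence, and section 6.5 then spells out what is blinded. A careful reader is soon corrected. This limits the harm, but the sentence still says *all*.
- **CRF1 is not named as the source of the secondary endpoints.** This is correct, and its stated uses are real-time monitoring of randomization and early start of follow-up. For ROSC, however, the other prehospital form, SRCR part 1, is also crew-reported, and no blinded source is described.
- **Research staff might later take the data from CRF1 without knowing the arm.** That would not blind a judgement the crew had already made, and the form itself carries the allocation.
- **Derivation rules commonly belong in an SAP, which is not shown.** This stands. The absence of such a rule is not the fault raised here. The fault is that the protocol asserts a property its design lacks.

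The text also tempts a reader to stronger inferences that it does not support.

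- *The main feasibility endpoint is compromised too.* Section 6.4 speaks of clinical endpoints. Shocks before randomization is a feasibility measure, a single proportion over all included patients, and the shocks are given before the card is drawn. Detection bias between arms does not arise.
- *Survival of the event is affected.* It is a CRF1 item, but not a listed endpoint.
- *Shock counts rest on the crew's memory.* The devices log shocks and their files are exported after each use.
- *The ROSC result may be biased by 10 points.* That is one patient's weight in the control arm, not an estimate of bias.

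**Conclusion.** The point holds in limited form. The blanket statement in section 6.4 is wrong for sustained ROSC. It is also wrong for the number of defibrillations to sustained ROSC, to the extent that the count stops at an unblinded ROSC call. It is right for the follow-up at 30, 90 and 180 days.

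The size of any bias is unknown, since the documents give no misclassification rate. The conclusion rests on one reading: that ROSC reaches the analysis through the crew-completed forms, the only sources the protocol describes as recording it. If ROSC were instead taken from another source by assessors unaware of allocation, the sentence could be true, but the protocol would have to say so.

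The pilot is not invalidated. No hypothesis testing is planned (section 7.4), and the feasibility aims are untouched. The correction still matters, because it changes what the trial can claim about detection bias in both secondary endpoints, which are meant to inform the main study.

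**What to change.** 1. In section 6.4, limit the blinding statement to the follow-up at 30, 90 and 180 days, in line with section 6.5. Add that prehospital endpoints, including ROSC, are ascertained by unblinded EMS personnel, and name detection bias beside performance bias.
2. State that shock counts, and the presence and timing of ROSC where the record allows, are taken from the exported defibrillator files and ambulance charts by one rule applied identically in both arms. Keep CRF1 as backup, and report how often it disagrees. Backup will be needed for shocks from another AED before EMS arrival, which the study devices cannot have logged. The detail of the rule can sit in the SAP.

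The cost is a wording change and a little more analysis of files and charts already being collected. The limitation is that the files can reveal DSD, so this reading is more objective but still not blinded, and the protocol should say so.

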## 6.5. Unblinding

This is an open label pilot trial. The neurological follow-up will be performed in a blinded way. That is the persons collecting the follow-up data at 30, 90 and 180 days will not be aware of the randomized allocation.

# 6.6. Description of the clinical procedures and diagnostic methods relating to the clinical investigation

[figure not shown]
The study is conducted in the prehospital emergency medical services, i.e. ambulance organizations. The trial will be conducted by participating ambulance units attending OHCA's. These units will perform screening for inclusion, randomization, intervention or control treatment and initial follow-up. All ambulance units in Sweden follow European resuscitation council (ERC) guidelines published in 2021 [4] and perform team training on an annual basis for high quality provision of ACLS care in OHCA.

In clinical practice a cardiac arrest is confirmed by the absence of consciousness and absence of normal or no breathing. In this clinical situation cardiac arrest shall be suspected and CPR initiated. In all cases of OHCA a defibrillator should always be attached with the standard pad placement first (A-L position) in accordance with standard of care and ERC guidelines. If there is VT/VF or an AED suggests defibrillation, defibrillation should be performed, and immediate chest compressions resumed.

Thereafter, the patient can be screened for inclusion. If two defibrillators study specific defibrillators on site, and no exclusion criteria the patient can be included and randomized. Randomization will be performed by drawing a scratch-card with concealed allocation that will be stored with the EMS defibrillators. All scratch-cards will be pre-randomized in a 3:1 ratio in blocks consisting of 4-8-12 and stratified by region and ambulance provider.

Version No: 1.1

Date: 2024-10-27 28 (48)

OHCA = Out of Hospital Cardiac Arrest, VT/VF = pulseless Ventricular Tachycardia / Ventricular Fibrillation, CPR = Cardiopulmonary Resuscitation, DSD = Double Sequence Defibrillation, CRF = Clinical Report Form

#### Defibrillator requirements:

In this study all participating EMS units will have corpuls3 defibrillators.

A perquisite for inclusion in this trial is that there are two study specific defibrillators on site, this means that either one EMS unit with two defibrillators (corpuls3) or two EMS units on site with one corpuls3 each.

In situations where the first EMS unit only has one defibrillator, but a second EMS unit arrives the patient can still be included as soon as the second defibrillator is on site. Therefore, in clinical practice the inclusion of patients will follow the flow-chart above.

If there is another defibrillator attached to the patient at EMS arrival (a public access AED or a AED from fire-fighters or police) that AED will be removed and the corpatch electrodes from

Version No: 1.1

Date: 2024-10-27 29 (48)

corpuls3 will be attached to the patient and connected to corpuls3 in all cases (this is in accordance with routine practice).

#### Intervention

If the patient is randomized to the intervention group, the ambulance crew team will apply the second defibrillator with electrodes placed in the A-P position as soon as possible. Defibrillation is performed by one person defibrillating both defibrillators in a sequential manner "Double Sequential Defibrillation" (DSD). All consecutive defibrillations will thereafter be performed with the DSD strategy until ROSC, termination of resuscitation or decision to move the patient to hospital.

#### Control

If randomized to the control group, the ambulance crew team will continue Advanced Life Support (ACLS) in accordance with standard of care. Defibrillation is performed with standard electrode placement using a single defibrillator. If an AED is the first defibrillator attached to the patient, the ambulance crew should shift from an AED to their own manual defibrillator, but the mode of defibrillation should remain in A-L position and only one defibrillation from one defibrillator should be used for each defibrillation and continue until ROSC, termination of resuscitation or decision to move the patient to hospital.

Follow up will be performed immediately after every resuscitation

- CRF1
- Swedish Register of Cardiopulmonary Resuscitation (SRCR) part 1, pre-hospital treatment, patient characteristics and short-term outcome.

At the hospital

- CRF2

Survival and neurological function at 30, 90 and 180 days.

## 6.7. End of the clinical investigation

The clinical investigation ends when the last subject has completed the last follow-up at 180 days. The sponsor will notify the Swedish Medical Products Agency within 15 days after the end of the clinical investigation and send the clinical investigation report within 1 year after the end of the clinical investigation including an easily understandable summary.

## 6.8. Monitoring plan

The clinical investigation will be monitored by an independent monitor before the clinical investigation begins, during the clinical investigation conduct, and after the clinical investigation has been completed, so as to ensure that the clinical investigation is carried out according to the CIP and that data is collected, documented, and reported according to SS-EN ISO 14155:2020 and applicable ethical and regulatory requirements. Monitoring is performed as per the investigation's monitoring plan and is intended to ensure that the subject's rights, safety, and well-being are met as well as data in the CRF are complete, correct, and consistent with the source data.

Please see appendix monitoring plan

## 7. Statistical considerations.

## 7.1. Analysis population

The principal analysis strategy will be on an "intention to treat" basis. All randomized patients will be included in this analysis.

Further analysis will be performed after exclusion of patients with post randomization exclusion criteria (such as not in cardiac arrest, not VT/VF or exclusion criteria that were not evident at the time of randomization) in a modified intention to treat (mITT) analysis.

### 7.2. Descriptive statistics

Version No: 1.1

Date: 2024-10-27 31 (48)

Descriptive statistics will be presented as counts and proportions for categorial variables. For continuous variables the mean and quartiles (Q1, Q3) will be presented. Balance between the treatment groups will be assessed using standardized mean difference.

## 7.3. Analytical procedures

The results will be presented as difference in proportions with 95% confidence intervals for categorial outcomes. For continuous outcomes the Wilcoxon rank-sum test will be used. In addition to these analyses, multilevel logistic regression analysis will be performed on categorial outcomes and multi-level ordinal regression for continuous outcomes. These results will be presented as odds ratios with 95% confidence intervals. The study site will be used as random effect.

## 7.4. Sample size calculation

No power or sample size calculation will be made in the pilot phase. The main reason is that it is a feasibility pilot study and no hypothesis testing will be performed.

The main purpose of the pilot study is to determine timely inclusion and randomization, measure adherence to protocol and assess safety aspects. The pilot study will also try to identify potential obstacles in conducting the study so they can be resolved prior to the main study.

The pilot phase of the study will continue until 40 patients (3:1 randomization) are included. The results from the pilot study will be of importance and used to inform a sample size calculation in a planned main study.

